#### **5.4.2 Discontinuation of Entire Study**

AbbVie may terminate this study prematurely, either in its entirety or at any study site, for reasonable cause provided that written notice is submitted in advance of the intended termination. The investigator may also terminate the study at his/her site for reasonable cause, after providing written notice to AbbVie in advance of the intended termination. Advance notice is not required by either party if the study is stopped due to safety concerns. If AbbVie terminates the study for safety reasons, AbbVie will immediately

notify the investigator by telephone and subsequently provide written instructions for study termination.

## **5.5 Treatments**

### **5.5.1 Treatments Administered**

Treatments administered during this OLE include upadacitinib 6 mg BID, 12 mg BID, (15 mg QD or 30 mg QD from January 2017). All subjects start treatment with 6 mg BID. Dose adjustments are allowed as described in Section 5.1.

Subject receiving 6 mg BID will dose with two 3 mg capsules twice a day.

Subjects receiving 12 mg BID will dose with one 12 mg capsule twice a day.

Subject receiving 15 mg QD will dose with one 15 mg tablet once a day.

Subject receiving 30 mg QD will dose with one 30 mg tablet once a day.

Study drug will be taken orally beginning at Baseline/Week 0 in OLE. Subjects will be instructed to take study drug at approximately the same times each day. The study drug can be taken with or without food. Subjects will continue their weekly stable dose of MTX and folic acid. AbbVie will not supply MTX or folic acid.

If a subject is unable to come to the study site to pick up their study drug due to state of emergency or any pandemic like COVID-19, a direct-to-patient (DTP) study drug shipment can be made from the study site to the subject if allowed by local regulations. AbbVie will submit any required notifications to the regulatory authority as applicable. Refer to Section 5.3.1.1 for details on DTP shipment of study drug.

Information about the Investigational Product is presented in Table 4.

**Table 4. Identity of Investigational Products**

Investigational Product	Upadacitinib	
Mode of Administration	Oral	Oral
Dosage Form	Capsule	Capsule
Strength (mg)	3	12
Mode of Administration	Oral	Oral
Dosage Form	Film coated Tablet	Film coated Tablet
Strength (mg)	15	30

#### **5.5.1.1 Packaging and Labeling**

Upadacitinib will be packaged in bottles containing 100 capsules or 100 tablets per bottle. Each bottle (kit) label will contain a unique kit number. This kit number is assigned to a subject via IRT and encodes the appropriate study drug to be dispensed at the subject's corresponding study visit. Each kit will be labeled as required per country requirements.

Labels must remain affixed to the bottles (kits) and must not be concealed by any over-labeling. All blank spaces on the label will be completed by site staff prior to dispensing to the subjects.

#### **5.5.1.2 Storage and Disposition of Study Drugs**

The study drug must be stored at controlled room temperature (15° to 25°C/59° to 77°F). The investigational products are for investigational use only and are to be used only within the context of this study. The study drug supplied for this study must be maintained under adequate security and stored under the conditions specified on the label until dispensed for subject use or returned to AbbVie.

#### **5.5.2 Method of Assigning Subjects to Treatment Groups**

This is an open-label study. The upadacitinib treatment is the same for all subjects so that there is no assignment of subjects to treatment groups. As a subject is confirmed for Baseline (Week 0) in OLE to be appropriate for participation in the study, the site will

enter the subject's number from Study M13-550 or Study M13-537, based on which study the subject was enrolled in, into IVRS (Interactive Voice Response System)/IWRS (Interactive Web based Response System) to obtain study drug. All eligible subjects will be assigned to upadacitinib 6 mg BID immediately after or up to 30 days following the Last Visit (Week 12) of Study M13-550 or Study M13-537 using an Interactive Voice Response System/Interactive Web Response System (IVRS/IWRS). Before the study is initiated, the telephone number and call-in directions for the IVRS/IWRS will be provided to each site. From Week 6 in OLE, subjects will receive subsequent treatment as described in Section [5.5.1](#).

### **5.5.3 Selection and Timing of Dose for Each Subject**

Subjects should take study drug as outlined in Section [5.5.1](#).

On scheduled study visit days, subject should follow their regular routine for study drug administration.

Each subject's dosing schedule should be closely monitored by the site at each study visit by careful review of the subject's dosing diary ([Appendix K](#)).

Capsule Formulation:

If a subject should forget to take his/her study drug dose at his/her regularly scheduled dosing time, he/she should take the forgotten dose as soon as he/she remembers the dose was missed as long as it is at least 6 hours before his/her next scheduled dose. If a subject only remembers the missed dose within 6 hours before next scheduled dose, the subject should skip the missed dose and take the next dose at the scheduled time.

Tablet Formulation:

If a subject should forget to take his/her study drug dose at his/her regularly scheduled dosing time, he/she should take the forgotten dose as soon as he/she remembers the dose was missed as long as it is at least 10 hours before their next scheduled dose. If a subject

only remembers the missed dose within 10 hours before next scheduled dose, the subject should skip the missed dose and take the next dose at the scheduled time.

If the subject experiences a study drug interruption > 30 days, they should notify their investigator, and the investigator will determine if study drug should be restarted or if the subject should be discontinued from the study.

Subjects who, in the opinion of the Investigator, develop adverse events that require study drug interruption and/or reach protocol specified toxicity management thresholds can have the study drug interrupted for up to 30 days while recovering from the adverse event.

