### **5.4 Removal of Subjects from Therapy or Assessment**

#### **5.4.1 Discontinuation of Individual Subjects**

A subject may withdraw from the study at any time. The Investigator may discontinue any subject's participation for any reason, including an adverse event, safety concerns or failure to comply with the protocol.

Subjects will be withdrawn from the study immediately if any of the following occur:

- Clinically significant abnormal laboratory results or adverse events, which rule out continuation of the study medication, as determined by the Investigator and the AbbVie Therapeutic Area Medical Director.
- Serious infections (e.g., sepsis) which would put the subject at risk for continued participation in the trial as determined by the Investigator in consultation with the AbbVie Therapeutic Area Medical Director.
- The Investigator believes it is in the best interest of the subject.
- The subject requests withdrawal from study drug or the study.

- Inclusion and exclusion criteria violation was noted after the subject started study drug, when continuation of the study drug would place the subject at risk as determined by the AbbVie Therapeutic Area Medical Director.
- Introduction of prohibited medications or dosages when continuation of the study drug would place the subject at risk as determined by the AbbVie SDP.
- Subject is non-compliant with TB prophylaxis (if applicable) or develops active TB at any time during the study.
- The subject becomes pregnant while on study medication.
- Subject has known malignancy, except for localized non-melanoma skin cancer. Discontinuation for carcinoma in-situ of the cervix is at the discretion of the Investigator.
- Subject is diagnosed with lupus-like syndrome, multiple sclerosis or demyelinating disease (including myelitis).
- Subject is significantly non-compliant with study procedures which would put the subject at risk for continued participation as determined by the Investigator.
- Subject has failed to achieve at least 20% improvement from Baseline (RCT period) in TJC and SJC with upadacitinib as described in Section 5.1.
- Confirmed diagnosis of deep vein thrombosis, pulmonary embolus or non-cardiac, non-neurologic arterial thrombosis.
- Subject develops a gastrointestinal perforation (other than due to appendicitis or mechanical injury).

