## 6.10 Toxicity Management

The toxicity management of the AEs including AEs of special interest consists of safety monitoring (review of AEs on an ongoing basis, and periodical/ad hoc review of safety issues by a safety data monitoring committee), interruption of study drug dosing with appropriate clinical management if applicable, and discontinuation of the subjects from study drug. The management of specific AEs and laboratory parameters is described below.

**Serious Infections:** Subjects should be closely monitored for the development of signs and symptoms of infection during and after treatment with study drug. Study drug should be interrupted if a subject develops a serious infection or a serious opportunistic infection. A subject who develops a new infection during treatment with study drug should undergo prompt diagnostic testing appropriate for an immunocompromised subject. As

appropriate, antimicrobial therapy should be initiated, and the subject should be closely monitored. Study drug may be restarted once the infection has been successfully treated. If study drug administration is interrupted for more than 30 days, the subject should be discontinued from the study. Subjects who develop active tuberculosis must be permanently discontinued from study drug.

**COVID-19:** Interrupt study drug in subjects with a confirmed diagnosis of COVID-19. Consider interrupting study drug in subjects with signs and/or symptoms and suspicion of COVID-19. The COVID-19 eCRF must be completed.

**Herpes zoster:** If a subject develops herpes zoster, consider temporarily interrupting study drug until the episode resolves.

**Gastrointestinal Perforation:** If the diagnosis of gastrointestinal perforation is confirmed, (other than appendicitis or mechanical injury) the subject must be discontinued from study drug.

**Cardiovascular Events:** Subjects presenting with potential cardiovascular events should be appropriately assessed and carefully monitored. These events will be reviewed and adjudicated by an independent Cardiovascular Adjudication Committee in a blinded manner.

**Thrombosis Events:** Subjects who develop symptoms of thrombosis should be promptly evaluated and treated appropriately. If the diagnosis of deep vein thrombosis, pulmonary embolus or non-cardiac, non-neurologic arterial thrombosis is confirmed, the subject should be discontinued.

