**Table 5. Specific Toxicity Management Guidelines for Abnormal Laboratory Values**

Laboratory Parameter	Toxicity Management Guideline
Hemoglobin	
 
• If hemoglobin < 8 g/dL, interrupt study drug dosing and confirm by repeat testing with new sample.
 
• If hemoglobin decreases <math>\geq 3.0</math> g/dL from baseline without an alternative etiology, interrupt study drug dosing and confirm by repeat testing with new sample.
 
• If hemoglobin decreases <math>\geq 3.0</math> g/dL from baseline and an alternative etiology is known, the subject may remain on study drug at the investigator's discretion.
 
• If confirmed, continue to withhold study drug until hemoglobin value returns to normal reference range or its baseline value.
 

Absolute neutrophil count (ANC)	
 
• If confirmed < 1,000/<math>\mu</math>L, interrupt study drug dosing until ANC value returns to normal reference range or its Baseline value.
 
• Discontinue study drug if confirmed < 500/<math>\mu</math>L by repeat testing with new sample.
 

Absolute lymphocytes counts (ALC)	
 
• If confirmed < 500/<math>\mu</math>L by repeat testing with new sample, interrupt study drug dosing until ALC returns to normal reference range or its Baseline value.
 

Total white blood cell count*	
 
• If confirmed < 2,000/<math>\mu</math>L by repeat testing with new sample, interrupt study drug dosing until white blood cell count returns to normal reference range or its Baseline value.
 

Platelet count	
 
• If confirmed < 50,000/<math>\mu</math>L by repeat testing with new sample, interrupt study drug dosing until platelet count returns to normal reference range or its Baseline value.
 

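### For a serious infection that interrupts study drug for more than 30 days, Protocol Section 5.5.3 leaves restart to the investigator while Section 6.10 says the subject should be discontinued

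*Protocol*

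**What the plan says.** Protocol Section 5.5.3 ends with two paragraphs on interruption, placed after the missed-dose instructions for capsules and tablets.

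- The first has a trigger that names no cause: "If the subject experiences a study drug interruption > 30 days, they should notify their investigator". Its consequence is that "the investigator will determine if study drug should be restarted or if the subject should be discontinued from the study".
- The second concerns subjects with adverse events that need an interruption, or who reach a toxicity threshold. They "can have the study drug interrupted for up to 30 days while recovering from the adverse event". The Synopsis repeats this paragraph but not the first one.

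Section 6.10, in its paragraph on serious infections, says "Study drug may be restarted once the infection has been successfully treated" and then "If study drug administration is interrupted for more than 30 days, the subject should be discontinued from the study".

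Section 6.10 also contains Table 5, which sets laboratory holds. For confirmed low hemoglobin, for example, the site is to "continue to withhold study drug until hemoglobin value returns to normal reference range or its baseline value".

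Section 5.4.1 lists the reasons for immediate withdrawal. Interruption beyond 30 days is not among them. Infection is listed as "Serious infections (e.g., sepsis) which would put the subject at risk for continued participation in the trial", to be judged by the investigator in consultation with the sponsor's medical director.

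**The concern.** Take a subject whose drug is stopped for a serious infection that needs more than 30 days to clear. Section 5.5.3 lets the investigator restart. Section 6.10 says the subject leaves the study. Section 5.4.1 makes withdrawal a joint judgement with the sponsor. The same clinical course could therefore end in re-exposure at one site and withdrawal at another.

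Long-term safety is part of the primary objective, and the choice feeds several planned outputs:

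- **Disposition** (SAP 7.0): whether the subject counts as discontinued.
- **Exposure and rates** (SAP 8.1 and 10.2.1): whether later treatment time and later events enter the rates per 100 patient-years.
- **Treatment-emergent status** (SAP 10.2): the window closes 30 days after the last open-label dose. An event starting more than 30 days into the hold falls outside the window if the subject is withdrawn. It falls inside if drug is later restarted, because the last dose then comes later.
- **Deviations** (Protocol 7.0, SAP 6.4): one category is a subject who met withdrawal criteria and stayed in. The text does not settle whether an interruption over 30 days is such a criterion.

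**Working it through.** There is no figure to recompute. The only number is the 30-day threshold, which is the same in the Synopsis, Section 5.5.3 and Section 6.10. The check sets the rules side by side by cause of the interruption.

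| Cause of an interruption over 30 days | 5.5.3, over-30-day paragraph | 5.5.3, final paragraph, and Synopsis | 6.10 and Table 5 | Result |
|---|---|---|---|---|
| Serious infection | Investigator chooses restart or discontinuation | Interruption permitted up to 30 days; nothing stated after that | Subject should be discontinued | Direct conflict |
| Other adverse event or toxicity threshold | Same choice, if the sentence covers these causes | Permitted up to 30 days; nothing stated after that | No 30-day rule; several holds run until recovery | Governing rule unclear |
| Cause other than an adverse event | Investigator chooses | Not addressed | No 30-day rule | No conflict |

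**Row 1.** The trigger in 5.5.3 covers every cause, so serious infection is included. The 6.10 sentence points to one outcome where 5.5.3 leaves two. There is no cross-reference in either direction. Section 5.4.1 does not break the tie, because it is silent on duration and treats serious infection case by case.

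**Row 2.** Table 5 shows that interruptions beyond 30 days are foreseeable. Holds for hemoglobin, neutrophils below 1,000/μL, lymphocytes, total white cells, platelets and creatinine end when the value recovers, with no stated limit. The UK versions in Appendix N do the same. Not every entry works this way: neutrophils confirmed below 500/μL lead to discontinuation, as do transaminase elevations that are unexplained or not resolving, and a CPK elevation without symptoms allows dosing to continue. For the open-ended holds, the site has a 30-day permission, an adjacent restart option of uncertain scope and a table that sets no limit.

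**Row 3.** Only one rule applies, so nothing needs reconciling.

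**The case against.** The strongest reply has four parts.

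1. **The specific rule prevails.** The 6.10 sentence is about serious infection and would override a general sentence elsewhere. That is a sensible way to read a protocol, but 5.5.3 names no exception and does not point to 6.10, so a site working from the dosing section would not know to apply it.

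2. **The over-30-day sentence in 5.5.3 is about missed doses.** It follows the missed-dose text and asks the subject to notify the investigator, which fits gaps the investigator did not order. This is plausible and would remove both problems. The sentence does not say so, however, and its trigger is not limited by cause.

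3. **The two 5.5.3 paragraphs can be read in sequence.** Up to 30 days is allowed; after that the investigator decides. This stands as a fair reading, and it is why the second problem is the weaker one. It does not help with serious infection, where 6.10 gives a different answer for the same period.

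4. **Table 5's silence on duration is not a contradiction.** Section 5.5.3 mentions the toxicity thresholds and may supply the limit. This also stands in part: the gap is that no text says what happens at day 31 of an open-ended hold.

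Three stronger readings are tempting and are not supported. A reader might infer that 6.10 requires discontinuation after any interruption over 30 days, but its sentence sits inside the Serious Infections paragraph. A reader might infer that 5.5.3 bars restart after 30 days for adverse events, but it is worded as a permission and states no consequence. A reader might infer that COVID-19 falls under neither rule, but Protocol 6.7 has COVID-19 infections captured as adverse events, so 5.5.3 reaches them, and a serious case also falls within the 6.10 infection paragraph.

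**Conclusion.** The conflict holds for serious infection: two sections of the current protocol give different instructions for the same event, and nothing states which governs. For other adverse events and toxicity thresholds there is a lesser inconsistency: a 30-day permission without a consequence, a restart option of unstated scope, and several laboratory holds without a limit. This is an internal inconsistency in the protocol, not a disputed design choice.

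The conclusion assumes that the over-30-day sentence in 5.5.3 means what it says and applies whatever the cause. If the sponsor intended it only for missed doses, the conflict disappears once that is written down.

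Size cannot be estimated. The documents report 494 subjects enrolled but give no count of interruptions over 30 days, by cause or overall. The effect on discontinuation counts, exposure and event rates may be small. The case for acting rests on inconsistent handling of subjects at the time of a serious infection and on the low cost of correction.

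**What to change.** Reconcile the Synopsis, Section 5.5.3 (both paragraphs), Section 6.10 including Table 5, and the UK tables in Appendix N. One stated rule should govern interruptions over 30 days, with any causes that follow a different rule named and cross-referenced. Align Section 5.4.1 with the result, so that it is clear whether such an interruption is a withdrawal criterion and hence whether continuing a subject is a deviation. Which rule to adopt is a clinical decision for the sponsor.

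The cost is a clarifying letter to sites or text in the next amendment. No new data or change to the analysis methods is needed. As an optional addition, a listing of subjects with interruptions over 30 days, giving cause and whether drug was restarted, would show readers of the study report how the existing text was applied.

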#### **5.5.4 Blinding**

This is an open-label study.

#### **5.5.5 Treatment Compliance**

The investigator or his/her designated and qualified representatives will administer/dispense study drug only to subjects enrolled in the study in accordance with the protocol. The study drug must not be used for reasons other than that described in the protocol.

Subject dosing will be recorded on a subject dosing diary ([Appendix K](#)). Subjects will be instructed to return all drug containers (even if empty) to the study site personnel at each clinic visit. The study site personnel will document compliance in the study source documents. Subjects will be counseled on missed doses of medication. If the subject does not return the dosing diary, used and unused study drug bottles the site should question the subject and obtain as much information as possible as to the dosing of the study drug.

The information should be documented on the source documents as per "best recollection" and when possible, re-verified when the dosing diary is returned before completing on the applicable eCRF page.

### **5.5.6 Drug Accountability**

The Investigator or his/her representative will verify that study drug supplies are received intact and in the correct amounts. This will be documented by signing and dating the Proof of Receipt or similar document and by registering the arrival of medication through the IRT. The original Proof of Receipt Note and the faxed IRT confirmation sheet will be kept in the site files as a record of what was received.

In addition, an IRT will be used to document investigational product accountability including but not limited to date received, the lot number, kit number(s), date dispensed, subject number and the identification of person dispensing the drug.

All empty/used study drug packaging will be inventoried by the site. Empty/used study drug packaging should be returned by the subject at each visit for accountability and compliance purposes and new packaging issued as necessary. Site staff will complete study drug accountability via IRT by using source documents, subject dosing diaries, and by visually inspecting the packaging whenever possible. After drug accountability and monitor reconciliation has been completed, used packaging and unused study drug will be destroyed on site according to local procedures or regulations or returned to the destruction depot (for those sites that do not meet AbbVie's documentation requirements for on-site destruction). The use of a third party vendor for drug destruction must be preapproved by AbbVie. For sites performing on-site drug destruction or using a third party vendor for drug destruction, a copy of the destruction methodology and date of destruction should be maintained at the site's facility.

Monitors will reconcile the site's processes, source documents, subject's dosing diaries, IRT or site accountability records, and destruction records to assure site compliance.

